3. STUDY DESIGN

3.1 Overview of Study Design

This is a local open-label, multi-centre Phase II study of the anti-tumoral activity of erlotinib (Tarceva[®]; 150 mg) evaluated by objective response rate (ORR) in patients with NSCLC in locally advanced or metastatic stages who have not received previous chemotherapy for their disease and who present activating mutations in the TK domain of the EGFR.

Summary of the study design is shown in Figure 1.

Figure 1 - Summary of study design

Rationale for Study Design

In this trial erlotinib is given in first-line treatment for advanced NSCLC.

Although this trial is non-randomized phase II trial, as Erlotinib is currently used in clinical practice to treat NSCLC it closely reflects clinical practice.

Any patient with locally advanced or metastatic non-small cell lung cancer disease found to have an EGFR Exon 19 deletion or exon 21 substitution L858R in the TK domain of EGFR gene will be offered first-line treatment with erlotinib.

The primary efficacy variable will be ORR.

Rationale for Dose Selection

The recommended daily dose of erlotinib was established at 150 mg, to be continued daily until disease progression.

All enrolled patients will receive recommended dose of erlotinib (150 mg/day). No dose escalation is permitted. Erlotinib dose will be reduced for toxicities as detailed in Section 6.1. Patients will be treated until progression of disease or unacceptable toxicity.

End of Study

This study is event-driven, with a recruitment period that will last until the end of March 2012 or until the number of patients aimed for the protocol (30) is achieved, whatever occurs first. Patients are to be treated until disease progression, unacceptable toxicity or patient request for discontinuation.

The study will end when the last patient has stopped erlotinib therapy and completed their last safety follow-up visit (28 days after last study drug administration). For all patients who have discontinued study drug treatment and are alive, information on survival will be collected.

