4.5 Concomitant Medication and Treatment

All concomitant medications and blood products administered to patients after the first dose of study drug, until 28 days after the last dose of study drug must be recorded on the electronic case report form (eCRF).

Permitted medication and therapies:

- Patients may receive non-myelosuppressive palliative radiation therapy if required. Concomitant radiation therapy with erlotinib treatment is allowed.
- Patients will receive full supportive care throughout the study, including transfusion of blood products, treatment with antibiotics, anti-emetics, anti-diarrheals, and analgesics as appropriate.
- Patients exhibiting dry eyes should be advised to use an ocular lubricant.

Not permitted:

- Administration of any other anti-cancer therapy (cytotoxic or biological/immunotherapy) is not permitted until after disease progression has been documented.
- Patients who have received study drug should not receive any other investigational drugs until after the post-treatment assessment (at least 28 days after the final dose of study drug).

Caution should be exercised when erlotinib is co-administered with CYP3A4 inhibitors and inducers. As grapefruit juice has the potential to inhibit CYP3A4 activity, patients should not eat grapefruit or drink grapefruit juice during the study.

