4.6 Criteria for Premature Withdrawal

Subjects have the right to withdraw from the study at any time for any reason.

In the case that the subject decides to prematurely discontinue study treatment [“refuses treatment”], he/she should be asked if he/she can still be contacted for further information. The outcome of that discussion should be documented in both the medical records and in the eCRF. If lost to follow-up, the investigator should contact the subject or a responsible relative by telephone followed by registered mail or through a personal visit to establish as completely as possible the reason for the withdrawal. A complete final evaluation at the time of the subject’s withdrawal should be made with an explanation of why the subject is withdrawing from the study.

When applicable, subjects should be informed of circumstances under which their participation may be terminated by the investigator without the subject’s consent. The investigator may withdraw subjects from the study in the event of intercurrent illness, adverse events, treatment failure after a prescribed procedure, lack of compliance with the study and/or study procedures (e.g., dosing instructions, study visits), cure or any reason where it is felt by the investigator that it is in the best interest of the subject to be terminated from the study. Any administrative or other reasons for withdrawal must be documented and explained to the subject.

If the reason for removal of a subject from the study is an Adverse Event, the Adverse Event will be recorded on the eCRF. The subject should be followed until the Adverse Event has resolved, if possible.

An excessive rate of withdrawals can render the study non-interpretable; therefore, unnecessary withdrawal of subjects should be avoided. Should a subject decide to withdraw, all efforts will be made to complete and report the observations prior to withdrawal as thoroughly as possible.

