5.6 Survival Follow-up Phase

After the final visit has been completed the patient should be followed every 6 months (\pm 15 days), or as appropriate evaluated by the investigator, for collection of subsequent therapies and survival status.

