Diarrhoea has been commonly observed (~ 50% patients) and is usually transient in nature. Previous trials have shown that the frequency and severity of diarrhoea rarely hindered administration of erlotinib and could be managed with loperamide. The recommended dose is loperamide 4 mg at first onset, followed by 2 mg every 2 – 4 hours until diarrhoea-free for 12 hours. Patients with diarrhoea should have regular monitoring of their electrolytes and be adequately rehydrated (see table 2 below). Prophylactic use of anti-diarrhoea treatments is not advised.

Table 4 - Guidelines for management of erlotinib-related toxic effects:

Toxicity	Grade	Guideline for management	Dose modification of erlotinib*
Keratitis	2	Interrupt the treatment. Ophthalmologic assessment.	Hold until recovery, and then restart at reduced dose. Continue regular ophthalmological assessments while on treatment.
	≥ 3	Discontinue treatment and seek ophthalmological advice	
Diarrhoea	1	Consider Loperamide (4 mg at first onset, followed by 2 mg every 2 – 4 hours until diarrhoea free for 12 hours) and appropriate rehydration.	None
	2	Loperamide (4 mg at first onset, followed by 2 mg every 2 – 4 hours until diarrhoea free for 12 hours) and appropriate rehydration.	Interrupt
	3	Interrupt and give appropriate rehydration, monitor electrolyte balance and renal function until resolution to Grade ≤ 1; restart at reduced dose.	Interrupt
	4	Discontinue treatment	
Rash	1	No intervention	None
	2	Any of the following: minocycline ^a , topical tetracycline or clindamycin, topical silver sulfadiazine, diphenhydramine, oral prednisone (short course)	None**
	3		Hold until recovery to ≤ grade 2, and then restart the dose.
	4	Discontinue treatment	
Other toxicity	≥ 2 prolonged clinically significant toxicity	Treatment as appropriate	Hold until recovery to ≤ grade 1, and then restart at reduced dose.

* If no recovery after 14 days of holding drug, patients should be discontinued from the study

** If dose has been previously held for grade 2 rash or diarrhoea, and grade 2 symptoms recur, or if the patient finds the symptoms unacceptable, hold dose until recovery to ≤ grade 1 and then reduce the dose.

^a Recommended dose: 200 mg p.o. b.i.d. (loading dose), followed by 100 mg p.o. b.i.d. for 7-10 days.

Rash:

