7.1.4 Progression of Underlying Malignancy

Progression of underlying malignancy is not reported as an adverse event if it is clearly consistent with the suspected progression of the underlying cancer as defined by RECIST criteria, or other criteria as determined by protocol. Hospitalization due solely to the progression of underlying malignancy should NOT be reported as a serious adverse event. Clinical symptoms of progression may be reported as adverse events if the symptom cannot be determined as exclusively due to the progression of the underlying malignancy, or does not fit the expected pattern of progression for the disease under study.

Symptomatic deterioration may occur in some subjects. In this situation, progression is evident in the subject's clinical symptoms, but is not supported by the tumour measurements. Or, the disease progression is so evident that the investigator may elect not to perform further disease assessments. In such cases, the determination of clinical progression is based on symptomatic deterioration. These determinations should be a rare exception as every effort should be made to document the objective progression of underlying malignancy.

If there is any uncertainty about an adverse event being due only to the disease under study, it should be reported as an AE or SAE.

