### 5.3.7 Tumour assessment

The absolute (n) and relative (%) frequencies of patients with a pre-existing CXR, a chest and upper abdomen CT Scan or MRI, an isotope bone scan, a brain CT Scan or a brain MRI will be described for each visit. For patients with any of these exams performed, the proportion of patients with abnormal clinically relevant exam results will be evaluated. Tumor assessment using the RECIST criteria (Appendix 5) will be carried at baseline, within +/- 5 days of the 8-weekly assessments and at the end of study treatment visit. For tumor assessments completed outside the scheduled time, results will be analyzed as part of the nearest scheduled visit.

Results on tumour assessment will be presented considering the ITT population.

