### Treatment period

**Response duration:** It will be measured from the time of initial response (CR/PR whichever is first recorded) until documented tumor progression (in weeks).

**Best overall response:** a categorical variable will be obtained, defined as the best response across all time points, according to RECIST 1.1, until end of study treatment. The following criteria will be considered:

Complete response – Patients who presented at least one complete response;

Partial response – Patients who not presented a complete response and presented at least one partial response;

Stable disease – Patients who not presented response (complete or partial) and presented at least one stable disease;

Progression disease – Patients who not presented response or stable disease and presented progression disease;

Inevaluable – All assessments are inevaluable.

**Objective response:** A dichotomous variable (yes/no) will be calculated. Patients who presented complete response or partial response as the best overall response will be classified in “yes”. Otherwise patients will be classified in “no”.

**Event PFS:** A dichotomous variable (yes/no) will be calculated. Patients who presented progression disease or death for any cause will be classified in “yes”. Otherwise patients will be classified in “no”.

**Time PFS:** Time between baseline visit and date of first occurrence of disease progression or death for any cause (in weeks) while the patient was under study or during the prolonged follow-up period. In patients where disease progression or death from any cause was not observed, the time will be censored at the date of last visit or last contact with the patient.

**Time overall survival:** The time from the first dose of erlotinib (assumed to be baseline visit) to the date of death due to any cause (in weeks). For patients alive at the end of the follow-up period, the time was censored at the date of last visit or last contact with the patient.

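### PFS is censored at last visit or last contact, although no scan is scheduled after end of treatment: the median is pushed upward if patients stop without progression and later progression is missed

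*SAP*

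**What the plan says.** **Censoring.** In SAP Appendix 3 (Treatment period), Time PFS for a patient without progression or death is handled thus: "the time will be censored at the date of last visit or last contact with the patient". Time overall survival ends at the same point. The protocol gives no PFS censoring rule.

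**Scans.** SAP 5.3.7 puts RECIST assessments at baseline, "within +/- 5 days of the 8-weekly assessments and at the end of study treatment visit". The Schedule of Assessments and SAP Appendix 2 agree and mark none later. The 28-day safety visit (Protocol 5.5) lists no tumour assessment. The 6-monthly contact (Protocol 5.6) is "for collection of subsequent therapies and survival status".

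**Stopping without progression.** Protocol 3.1 allows treatment to end for toxicity or at the patient's request. A patient who refuses treatment is not automatically lost: "he/she should be asked if he/she can still be contacted for further information". A Table 4 footnote adds a further route: "If no recovery after 14 days of holding drug, patients should be discontinued from the study". Follow-up then continues: "For all patients who have discontinued study drug treatment and are alive, information on survival will be collected".

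**Events.** SAP 5.3.9.2 and Appendix 3 count progression and death both on study and in the later follow-up.

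**The concern.** Last contact is the right censoring date for survival, because any contact establishes that the patient is alive. For PFS the matching date is the last one on which absence of progression was checked. Between the end-of-treatment scan and the last contact, a patient who stopped without progression sits in the PFS risk set while death is the only event that a scheduled procedure would reveal. If such a patient progresses unseen, the Kaplan-Meier curve stays too high until death.

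Patients who decline contact or are lost matter little, because their last contact is close to their last scan. Patients still on treatment matter little too, since visits and scans coincide.

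What is at stake is the reported median PFS. It is an interim result (SAP 5.5), and Protocol 3.3 gives comparison with published data as the reason for the interim analysis. The erlotinib medians cited in Protocol 1.3 are 12.5, 13.1 and 14.0 months.

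**Working it through.** The documents state no PFS figure to reproduce.

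**1. Ordering of the two rules (no assumptions).** Kaplan-Meier is S(t) = ∏(1 − d_j/n_j). Hold the progression and death events fixed, so every d_j is the same under both rules. Moving a censoring date later can only raise n_j, so each factor, and hence S(t), is at least as large. The median under the SAP rule is therefore never below the last-scan median.

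**2. Bias against the truth, continuous detection.** Inputs:
- True median PFS 12.5 months (pooled first-line erlotinib, Protocol 1.3 Table 2; its use here is an assumption). λ = ln 2/12.5 = 0.0555 per month.
- Stopping without progression at a constant rate μ, unrelated to prognosis, as a lifetime share p (assumed 10% or 25%). μ = λp/(1 − p) = 0.0062 or 0.0185. Share stopped by 12 months: p(1 − e^(−12(λ+μ))) = 5.2% or 14.7%.
- Capture q of later progression: 0, 50 or 100% (assumed).
- Median survival after progression 8 to 18 months (assumed).
- No data cut-off before 18 months (assumed). The planned end of recruitment, March 2012, and the interim cut-off of 30 September 2013 are 18 months apart.

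Without a cut-off before the median, the SAP-rule curve is the share with no observed event:

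S_SAP(t) = e^(−λt) + (1 − q)·A(t),

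where A(t) is the share who stopped, have since truly progressed and are still alive. The second term is the bias. It is zero if nobody stops (A = 0) or if capture is complete (q = 1).

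At 12.5 months, A = 0.0115 to 0.0140 for 10% stopping and 0.0327 to 0.0399 for 25%. With q = 0 the curve therefore reads 0.511 to 0.514, or 0.533 to 0.540, where the truth is 0.500. Solving S_SAP(t) = 0.5 gives the SAP column below. The last-scan column comes from simulation (1,000,000 patients per scenario, cut-off uniform over 18 to 30 months, deaths kept as events, no later scan in event-free stoppers).

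| Stopping | Capture | SAP rule, months | Bias | Last-scan rule, months | Bias |
|---|---|---|---|---|---|
| 10% | 0% | 12.9–13.0 | +0.4 to +0.5 | 12.54–12.58 | 0 to +0.1 |
| 10% | 50% | 12.7–12.8 | +0.2 to +0.3 | 12.40–12.44 | −0.1 |
| 10% | 100% | 12.5 | 0 | 12.29–12.33 | −0.2 |
| 25% | 0% | 13.9–14.3 | +1.4 to +1.8 | 12.65–12.67 | +0.2 |
| 25% | 50% | 13.1–13.3 | +0.6 to +0.8 | 12.25–12.28 | −0.2 |
| 25% | 100% | 12.5 | 0 | 11.95–11.96 | −0.5 |

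Simulated SAP medians agree with the formula to within about 0.05 months. At 10% stopping and 0% capture they run to 13.07, which is +0.6 after rounding. A repeat of the last-scan run at 25% stopping and full capture gave 11.92 to 11.94, so its downward bias there is 0.5 to 0.6.

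**3. The actual 8-weekly grid.** Progression is dated at scans 56 days apart (56/30.4 = 1.8 months), so the median moves in steps. Simulated medians in months; the reference is the same grid with no stopping:

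| True median | Reference | SAP, 10% stop, 0% capture | SAP, 25% stop, 50% capture | Last-scan, 25% stop, 50% capture |
|---|---|---|---|---|
| 12.5 | 13.0 | 13.6–14.6 | 13.8–14.6 | 12.9 |
| 13.1 | 14.60 | 14.68 | 14.70–14.72 | 13.0 |
| 14.0 | 14.74 | 14.85 | 14.88 | not run |

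At a true 14.0 with 25% stopping and 0% capture, the SAP rule gives 16.55. The shift can be almost nothing or a full step, and at 13.1 the last-scan rule has the larger error, downward.

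**The case against.** **Progression may well be captured.** Other anti-cancer therapy "is not permitted until after disease progression has been documented". Protocol 7.1.4 says that "every effort should be made to document the objective progression of underlying malignancy", and RECIST section 4.4 in Protocol Appendix 1 extends that effort beyond treatment. The SAP accepts progression found in follow-up. If sites comply, capture is high, the SAP rule is close to unbiased and last-scan censoring errs downward. This stands, and it is why the conclusion is conditional. But these are exhortations: no visit schedules the detection, and nothing the SAP reports would show what capture was.

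**Routine post-treatment scans are not expected here.** RECIST section 4.5 ties them to trials whose main endpoint is a time to event; here it is ORR. That answers a criticism of the scan schedule. It does not justify treating unscanned time as progression-free.

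**Last-scan censoring is not clean either.** It keeps stoppers who later progress and drops event-free stoppers at their last scan, hence its downward bias at high capture. If stopping is related to prognosis, both rules can err. With the hazard assumed to triple after stopping (25% stopping, true median 11.0), last-scan gives 12.4–12.6, 11.7 and 10.9 at 0, 50 and 100% capture; the SAP rule gives 13.0–13.8, 11.9–12.2 and 11.0. This stands, and argues for showing both.

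**The consequence is small.** PFS is secondary, no hypothesis is tested (Protocol 8.2.2), and a single trial of 30 had simulated medians from about 7 to 20 months. This limits the weight of the point; it does not make the rule right.

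**Conclusion.** The point holds conditionally. The SAP gives PFS the survival censoring rule, no scan is scheduled once treatment ends, and the rule can only place the median at or above the last-scan median on the same events. Upward bias needs both stopping without progression and incomplete capture of later progression.

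The sizes in the working rest on the assumed 12.5-month median, constant rates, unrelated stopping and, in step 2, continuous detection. They are illustrations, not forecasts.

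A reader might infer three stronger things that the documents do not support:
- *That median PFS will be inflated.* Neither the stopping rate nor the capture rate is given, and at full capture the SAP rule is the unbiased one.
- *That there is a general capture rate above which the SAP rule is better.* On the 8-weekly grid this depends on where the median falls between scans.
- *That the SAP median would be higher in a quotable share of trials of 30.* That share turns on how the median is defined when the curve equals exactly 0.5.

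The change should be made because it is cheap and the present rule hides its own weakness. It affects an estimate meant for comparison with published medians. It affects neither ORR nor any decision.

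**What to change.** In SAP Appendix 3, Time PFS:
1. Censor patients without documented progression or death at the date of their last evaluable tumour assessment, counting unscheduled and post-treatment assessments, or at baseline if there is none. Keep death from any cause as an event.
2. Report the current last-contact rule beside it as a sensitivity analysis.
3. Add a count of patients who stopped without progression, split into later documented progression, later assessment without progression, and neither. This lets a reader judge capture, and so which median to trust.
4. Leave overall survival censoring unchanged.

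Separately, reconcile the wording on the last scan. Protocol 5.3 (scheduling of tumour assessments) mentions one at an end-of-study visit while deferring to the Schedule of Assessments, and SAP Table 8 has an end-of-study column. The Schedule, SAP Appendix 2 and SAP 5.3.7 show no scan at the 28-day visit. One scan at 28 days would not cover the months of follow-up after it.

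Cost: a few lines of SAP text, one more Kaplan-Meier run and one small table, from assessment dates that PFS and response duration already need. The confidence interval becomes slightly wider, and the new primary rule errs downward if later progression is well captured, so both results should be shown.

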5.3 Clinical Assessments and Procedures

Testing for EGFR mutation will be performed only at Screening. All of the other clinical and safety assessments will be performed at Screening, Baseline and on Day 1 of every 8th week until PD, death, or unacceptable toxicity, as indicated in the Schedule of Assessments. For all patients who have discontinued study drug treatment and are alive, information on further therapy for NSCLC and survival will be collected.

Tumor Response Criteria

Tumor response will be evaluated according to the RECIST criteria (Eisenhauer et al., 2009) (see Appendix 1).

In this study, tumour response will be measured using computer tomography (CT) or magnetic resonance image (MRI) scans of the chest and upper abdomen, for imaging of liver and adrenal glands. Patients known to have bone metastasis or displaying clinical or laboratory signs (e.g. serum alkaline phosphatase (ALP) > 1.5 ULN) of bone metastasis should have an isotope bone scan at baseline. In cases where there are suspected brain metastases, CT scanning of the brain will be performed.

Post-baseline assessments are to be performed within +/- 5 days for the 8 weekly assessments. If there is suspicion of disease progression based on clinical or laboratory findings, a tumour assessment should be performed as soon as possible, before the next scheduled evaluation.

Consistency of consecutive CT-scans, X-rays or MRIs should be ensured during all assessments for each patient, with the same technique being used for evaluating lesions throughout the treatment period. The use of spiral CT or MRI is required for baseline lesions of < 20 millimetres (mm) and must be documented in medical records and used consistently throughout the study. The use of oral and IV contrast etc. should, as long as it is clinically possible, be kept consistent. Tumor measurements should be made by the same investigator/radiologist for each patient during the study to the extent that this is feasible.

Scheduling of tumour assessments

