8.2.7 Interim Analysis

One interim analysis is planned for the study with a cut-off date on 30th September 2013. This interim analysis will include an epidemiological, efficacy and safety characterization of erlotinib in 1st line EGFR Mut+ mNSCLC Portuguese population.

Interim analysis will include the following descriptive analyses:

Characterization - demographics, medical history, Eastern cooperative oncology group performance status, clinical response (RECIST criteria).

Efficacy – Best Overall response, progression free survival, overall survival and epidermal growth factor receptor. Additionally, PFS will be obtained for Exon 19 and Exon 20 (if applicable).

Safety – Drug compliance, adverse events (incidence of AE and SAE, incidence of AE and SAE with remote, possible or probable relationship with study drug, description of AE and SAE, SAE with remote, possible or probable relationship with study drug) and subsequent therapy for NSCLC.

Analysis will be conducted according to the definitions described in section 8.1 and considering the populations described in section 8.2.1. ▮

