### **5.3.9.2 Secondary Efficacy Endpoints**

The secondary efficacy variables include:

- Progression-free survival (PFS), defined as the time from baseline visit to the date of first occurrence of disease progression or death for any cause while the patient was under study or during the prolonged follow-up period. PFS will be summarized as median time and will be estimated using the Kaplan-Meier method. Ninety five percent (95%) confidence interval will be estimated for median time to PFS.
  
- Overall survival (OS), defined as the time from the first dose of erlotinib to the date of death due to any cause while the patient was under study or during the prolonged follow-up period. Overall survival variable will be summarized as median time to OS and will be estimated using the Kaplan-Meier method. 95% confidence interval will be estimated for median time to OS. The date of first dose is not captured in the study CRF. Therefore, for this endpoint it will be assumed that the patient will take the first dose at the day of the baseline visit.
  
- Epidermal growth factor receptor (EGFR) mutation frequency. The presence of EGFR mutation (exon 19 deletion and/or exon 21 substitution L858R) in the study population will be presented as the relative frequency of those mutations among the total screened patients. A 95% confidence interval will be estimated for this value using binomial distribution.
  
- Response duration, defined as the time of initial response (CR/PR whichever is first recorded) until documented tumor progression. Response duration will be summarized as median time and will be estimated using the Kaplan-Meier method. Ninety five percent (95%) confidence interval will be estimated for median time to response duration.

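### OS censors survivors at their last contact and no survival check is tied to a cut-off, so late OS may read low at the interim if deaths become known between scheduled contacts

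*SAP*

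**What the plan says.** **Censoring.** SAP Appendix 3 (Time overall survival) says: "For patients alive at the end of the follow-up period, the time was censored at the date of last visit or last contact". SAP 5.3.9.2 counts time "to the date of death due to any cause while the patient was under study or during the prolonged follow-up period". No end date is given for that prolonged period.

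**Contact schedule.** On treatment, Protocol 5.3 schedules assessments at "Baseline and on Day 1 of every 8th week until PD, death, or unacceptable toxicity". Protocol 5.5 adds a safety visit 28 days after the last dose. After that, Protocol 5.6 says: "After the final visit has been completed the patient should be followed every 6 months" (window 15 days either way), "or as appropriate evaluated by the investigator, for collection of subsequent therapies and survival status".

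**Cut-offs.** Protocol 8.2.7 says: "One interim analysis is planned for the study with a cut-off date on 30th September 2013". No cut-off is stated for the final analysis. Protocol 3.1 adds: "For all patients who have discontinued study drug treatment and are alive, information on survival will be collected". It attaches no date and no status check to this.

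**Deaths after last contact.** SAP Appendix 4 imputes a death known only by year when that year is later than the year of last contact. Deaths dated after last contact are therefore counted.

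**The concern.** Deaths and survivors can end up with different horizons. A patient in survival follow-up who is alive at the cut-off may last have been contacted up to about 6.5 months before it (6 months plus the 15-day window), and is censored there. If another patient dies in the same gap and the site hears of it, that death is an event. The Kaplan-Meier risk set in that stretch then loses survivors but keeps deaths, and estimated survival there is too low.

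The interim is where this could matter. Protocol 4.4 plans recruitment to the end of March 2012, only 18 months before the interim cut-off. OS is among the interim results, and Protocol 3.3 gives comparison with published data as the purpose. Even without bias, follow-up that a phone call would recover is discarded in a 30-patient study.

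**Working it through.** **The plan's own figures.** The documents give no precision or event count for OS, so there is no OS figure to reproduce. Their two sample-size figures do reproduce. The ORR margin 1.96 × √(p(1−p)/30) is 17.9 points at p = 0.5 and 17.5 at p = 0.60. The smallest n with 0.1n − 1.96√(0.09n) ≥ 30 is 421, against the stated 420. Neither bears on OS.

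**Which part of the curve can be affected.** If contacts keep to their windows, no survivor is censored more than about 6.5 months before the cut-off. Follow-up times shorter than (minimum follow-up − 6.5 months) are therefore untouched:

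- Interim, 18 months after recruitment ends: 18 − 6.5 = 11.5 months.
- Cut-off 36 months after recruitment ends: 36 − 6.5 = 29.5 months.

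**Size by simulation.** Inputs from the documents are visits every 8 weeks on treatment, a safety visit at 28 days, contact every 6 months afterwards, and 18 months from planned end of recruitment to the interim. Time on treatment has a median of 12.5 months, the pooled first-line PFS in Protocol 1.3; using 13.1 months instead changes the results by less than 0.1 month. Assumptions not in the documents are exponential OS with a median of 12 to 30 months, uniform recruitment over 12, 15 or 18 months, and how deaths become known.

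Three rules were compared in large samples:

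- A: survivors censored at the cut-off.
- B: every death up to the cut-off known, survivors censored at last scheduled contact.
- C: deaths and survivors both known only through scheduled contacts.

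Shift in the Kaplan-Meier median (months) at interim timing:

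| True median | B − A, 12-month recruitment | B − A, 15-month | B − A, 18-month | C − A, 12- or 18-month |
|---|---|---|---|---|
| 12 | 0 | 0 | 0 | 0 |
| 18 | 17.67 − 17.97 = −0.3 | about −0.2 | 17.83 − 18.03 = −0.2 | about 0 |
| 24 | 22.40 − 24.10 = −1.7 | 22.7 − 24.0 = −1.3 | 22.90 − 23.97 = −1.1 | −0.3 to −0.1 |
| 30 | A not reached; B 26.0 | about −3 | 27.56 − 29.97 = −2.4 | A not reached, C 28.6; or −0.3 |

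Further results:

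- With 15-month recruitment and a true median of 24 months, 24-month survival falls from about 50.0% to 47.7% under B.
- If half of the gap deaths are known, roughly 60% of the shift remains (somewhat more at a true median of 30).
- With 36 months to cut-off, the median does not move in any scenario.
- Survivors are censored on average 2.3 to 2.4 months before the interim cut-off, and 18-month survival falls by at most 0.006.
- Follow-up lost is about 4–7% at the interim and 2–4% with 36 months to cut-off.
- In trials of 30 patients (12-month recruitment, rule B) the mean shift in the median is −0.1 to −0.8 month, against a sampling SD of 3.3 to 3.9. That average covers only trials in which both rules reach a median. Rule B also reaches one too often: 80% of trials against 69% at a true median of 24.

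**The case against.** A reader might infer that OS is simply biased low because deaths count to the cut-off and survivors do not. The documents do not support that. Protocol 5.6 collects survival status, dead or alive, at the same contacts. Protocol 7.2.3 keeps deaths from progression out of SAE reporting, and footnote e of the Schedule of Assessments limits SAE collection after the safety visit to drug-related events. Nothing therefore requires most late deaths to be reported between contacts. The 24-hour route in Protocol 7.2.2 covers other fatal events only. Appendix 4 shows that deaths after last contact count, not when they are learned. **This stands**, and makes the bias conditional.

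It is also tempting to read contact as only 6-monthly throughout. That ignores the 8-weekly visits on treatment, the safety visit and the investigator's discretion. **This stands**: 6.5 months is a worst case, and the average gap is much shorter.

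The final analysis may be hardly touched. The study ends after the last patient stops erlotinib. With exponential treatment times of median 12.5 months, the longest of 30 averages (12.5 / ln 2) × 3.995 ≈ 72 months, which puts a median of 24 or 30 months well inside follow-up. **This stands under that assumption**, but no final cut-off is stated.

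Lastly, censoring at last contact is an ordinary convention, and a call at the cut-off would itself be a last contact. OS is secondary, the interim is descriptive and no hypothesis is tested. **This limits the weight of the point but does not remove it.** The rule speaks of patients alive at the end of follow-up, yet neither document provides the step that would establish this.

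**Conclusion.** The point holds as a gap in the plan with a conditional consequence. Survivors are censored at last contact, contact after treatment is sparse, and no survival check is tied to the interim or to a stated final cut-off.

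OS may be biased low, late in the curve and mainly at the interim, if deaths become known between scheduled contacts. With all such deaths known, 15-month recruitment, exponential OS and interim timing, the median shift runs from 0 (true median 12 months) to about 3 months (true median 30). The shift is close to nil if deaths are learned only at scheduled contacts or if the median lies well inside follow-up. True OS, the recruitment span and the share of gap deaths known early are all assumptions. A certain downward bias should not be inferred. The loss of some follow-up does not depend on how deaths are learned. This is a cheap improvement to a secondary endpoint; no decision rule in the plan rests on it.

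**What to change.** In Protocol 5.6 and SAP Appendix 3 (Time overall survival):

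1. State a data cut-off for the final analysis alongside the interim one.
2. Around each cut-off, have sites confirm the survival status of every patient not known to be dead, by call or record check.
3. Count only deaths on or before the cut-off.
4. Censor patients confirmed alive at or after the cut-off on the cut-off date.
5. Use last contact only for patients who cannot be reached.

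The cost is at most 30 calls or record checks per cut-off and a few sentences of text. The 6-monthly schedule can stay as it is.
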